10.2 Sample size

The severity of the FLS expressed as the patient's judgement on a VAS ranging between 0 and 10 is the parameter used to calculate the sample.

The clinical hypothesis is that four hours after administering IFN β , the average difference (d) of the VAS score between the two treatments is equal to or greater than 0.50, where d is expressed in standardized units.

Where $\mu_{Cetir.}$ is the mean VAS score obtained after administration of the standard therapy (SOT) plus cetirizine, and $\mu_{NoCetir}$ is the mean obtained after administration of the standard therapy alone (SOT), the difference between the two treatments will be expressed as:

$$d = \left| \mu_{\text{noCetir.}} - \mu_{\text{Cetir.}} \right| / \sigma = 0.50$$

where d is the effect size expressed in standard units and σ is the standard deviation of the difference.

Therefore the null hypothesis (two tailed) is

H0: $\left| \mu_{\text{noCetir.}} - \mu_{\text{Cetir.}} \right| / \sigma \leq 0.50 - \text{ or d=0}$;

While the alternative hypothesis is

Ha: $|\mu_{\text{noCetir.}} - \mu_{\text{Cetir.}}|/\sigma| > 0.50 - \text{ or } d \neq 0.$

Selecting * = 0.05 and β = 0.20 (power =80%), it is necessary to enrol 34 patients, who will be sequentially treated in accordance with a crossover design, as shown in the randomisation list.

Taking into consideration the possibility of a 15-20% drop-out rate, the sample to be randomised for the two sequences will be made up of 40 subjects.

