Inclusion/ Exclusion criteria	 Inclusion criteria Patients of both genders. Patients between the ages of 18 and 55 years old. Patients with Relapsing-Remitting Multiple Sclerosis (RRMS). IFNβ 1a treatment (IM or SC) or 1b for at least 3 months. Pregnancy test with negative result carried out no more than 30 days from the baseline visit (if applicable) FLS-S ≥ 2 despite standard therapy (SOT) for FLS. Ability to provide written informed consent for participating in the study. Patients must not present with clinically significant conditions or circumstances, with the exception of MS, which in the opinion of the Investigator may interfere with study evaluations or participation in the study. Use of effective contraception or being in menopause for at least 6 months (where applicable) Exclusion criteria Potentially fertile patients (male or female) who are not using contraception. Women who are pregnant or breastfeeding. Known intolerance or contraindications for cetirizine use. Known hereditary condition of intolerance to galactose, Lapp lactase deficiency, glucose-galactose malabsorption 		
Sample size	The severity of the FLS expressed as the patient's judgement on a visual analogue scale (VAS) ranging between 0 and 10 is the parameter used to calculate the sample. The clinical hypothesis is that four hours after administering IFN, the average difference (d) of the VAS score between the two treatments is equal to or greater than 0.50 where d is expressed in standardized units. Selecting $\alpha=0.05$ and $\beta=0.20$ (power =80%), it is necessary to enrol 34 patients, who will be sequentially treated in accordance with a crossover design, as shown in the randomisation list. Taking into consideration the possibility of a 15-20% drop-out rate, the sample to be randomised for the two sequences will be made up of 40 patients.		
Statistical analysis	The observations will be made before the IFN injection, 4 hours after and 12/15 hours after the injection. • Descriptive analysis All the variables recorded in the Case Report Form will be reported in descriptive tables. In particular, continuous variables will be reported as a mean and SD, while nominal or discrete variables will be summarized in contingence tables. • Uniformity of the sequences to the baseline.		

	Evaluation of the efficacy variables.

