10.3.8 Criteria for evaluation of data

In regards to efficacy, all randomised patients who have taken at least one dose of antihistamine and of placebo and who have had at least one pre and post drug evaluation for both products will be evaluated, in accordance with the crossover design Intention-To-Treat. Patients who do not meet these four requirements may not be evaluated for efficacy.

On the other hand, those patients who took at least one dose of antihistamine or one of placebo will be evaluated for safety.

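### Forty randomised patients allow for at most 15% lost from the efficacy analysis; at the 20% end of the stated range, 32 could remain and power would be about 78%, a minor shortfall

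*Protocol*

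**What the plan says.** The outline (Sample size row) and section 10.2 give the same justification. The primary measure is the FLS-VAS score four hours after interferon, and the hypothesis is that "the average difference (d) of the VAS score between the two treatments is equal to or greater than 0.50" in standardised units. Section 10.2 adds the scaling: "where d is the effect size expressed in standard units and σ is the standard deviation of the difference". The test is two-tailed at 0.05 with β = 0.20, and the result is that "it is necessary to enrol 34 patients, who will be sequentially treated in accordance with a crossover design".

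Both places then move from 34 to the number randomised. Section 10.2 cites the "possibility of a 15-20% drop-out rate, the sample to be randomised for the two sequences will be made up of 40 subjects". Neither place gives an inflation formula.

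Section 10.3.8 defines the efficacy population: at least one dose of each product, and at least one evaluation before and one after the drug for each. It adds: "Patients who do not meet these four requirements may not be evaluated for efficacy".

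**The concern.** The sentence offers 40 as the allowance for a drop-out rate of 15% to 20%, so a reader takes it that at least 34 patients will remain anywhere in that range. That is so at 15%. At 20%, if the drop-outs contribute nothing to the efficacy comparison, 32 remain, which is fewer than the number the protocol calls necessary. Since 34 is the smallest number that reaches 80%, the base figure has no slack to absorb this.

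What is at stake is the accuracy of the sample-size statement: the stated 80% power is not secured at the upper end of the drop-out range the protocol itself names. The design and the analysis are not affected.

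**Working it through.** **Inputs, all from the protocol**

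- Two-sided α = 0.05 and target power 80% (outline and section 10.2).
- d = 0.50, scaled by the standard deviation of the within-patient difference (section 10.2). The null value tested is taken as d = 0.
- Required number 34; randomised 40; drop-out 15–20% (outline and section 10.2).
- Efficacy population: section 10.3.8.

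**Step 1: reproduce 34.** For a paired t-test on n within-patient differences, the statistic follows a noncentral t distribution with n − 1 degrees of freedom and noncentrality d√n. Power is the probability that it falls beyond ± the 97.5% point of the central t. For n = 34 the noncentrality is 0.50 × √34 = 2.915 and the critical value is 2.035.

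| Evaluable n | Power, n − 1 df | Power, n − 2 df (two-sequence crossover) |
|---|---|---|
| 32 | 78.2% | 78.1% |
| 33 | 79.5% | 79.5% |
| 34 | 80.8% | 80.7% |
| 35 | 82.0% | 81.9% |

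Under either choice 34 is the smallest n with power of at least 80%, so the protocol's base number is reproduced.

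**Step 2: patients left from 40.**

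- 15% lost: 40 × 0.85 = 34
- 17.5% lost: 40 × 0.825 = 33
- 20% lost: 40 × 0.80 = 32

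**Step 3: number needed to keep 34.**

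- 15%: 34 / 0.85 = 40
- 20%: 34 / 0.80 = 42.5, so 43, or 44 for equal sequences

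The cruder inflation 34 × 1.20 = 40.8 rounds up to 41, so neither method gives 40 at the 20% end.

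**Step 4: size of the shortfall.** With 32 evaluable, power is 78.2%. That is 80.0 − 78.2 = 1.8 points below the stated power, and 80.8 − 78.2 = 2.6 points below the power with 34. The standardised difference detectable with 80% power at n = 32 is 0.511, against the planned 0.50.

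**Step 5: are drop-outs and non-evaluable patients the same?** No. Section 5.1 has the scores recorded at every injection, and section 10.3.8 asks only for one dose and one before-and-after pair on each product. A patient who leaves in period 2 after one scored injection therefore meets the rule, provided the diary is recovered. At 20% drop-out, 40 × 0.20 = 8 patients leave; if two of the eight leave at that stage, 32 + 2 = 34 remain evaluable. The figure of 32 needs all eight to be non-evaluable.

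**The case against.** The strongest counter-argument is the one in step 5: drop-out is not the same as loss from the efficacy analysis. The protocol gives no timing of drop-out, so the following is only an illustration. Suppose drop-out is uniform over the eight weeks and the first scored period-2 injection falls as late as one week into that period. Then 3/8 of the eight drop-outs, or three patients, stay evaluable; 35 remain and power is 82.0%. This stands, and it rules out the stronger readings that a reader might infer: that the allowance fails for every drop-out rate above 15%, or that 20% drop-out necessarily leaves 32. The protocol supports neither. One limit applies: section 10.3.4 refers to evaluation after four weeks of therapy, and an endpoint read strictly that way could lose more patients. Section 10.3.8 is nevertheless the stated rule for who is evaluated.

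Four further arguments carry less weight.

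- **The wording is loose.** The protocol says that drop-out was considered, and does not expressly promise 80% power over the whole range. Six extra patients are 6/40 = 15.0% of those randomised and 6/34 = 17.6% of those required, both inside the range. Even so, the sentence presents 40 as the allowance for 15–20%, and 20% is part of that range.
- **A normal approximation gives 80.7% power at 32.** That is correct, but the same approximation gives a requirement of ((1.96 + 0.8416)/0.50)² = 31.4, so 32 and not the stated 34. The paired t-test is the method that reproduces 34.
- **Drug is supplied for 10 reserve patients (section 8.2.1).** No replacement rule is stated, and randomisation numbers run from 01 to 40 (section 8.4), so the reserve does not settle the matter.
- **This is a pilot study and the effect on power is small.** Both are true, and they bear on how much weight the point deserves. The protocol still makes a formal 80% power statement, which should agree with its own figures.

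**Conclusion.** The point holds in a limited form and is minor. Forty randomised patients keep 34 evaluable if no more than 15% are lost from the efficacy analysis. If 20% are lost, 32 remain and power is about 78% for d = 0.50, up to two patients short and about 1.8 points below the stated 80%.

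This rests on the protocol's own d, α and number of 34, on a two-sided paired t-test (one degree of freedom fewer changes power by about 0.1 point), and, for the figure of 32, on every drop-out being non-evaluable under section 10.3.8. That last condition is the worst case.

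A reader might go further and conclude that the trial is underpowered or must enrol more patients. The documents do not support that: the lower end of the range is met exactly, some period-2 drop-outs remain evaluable, and the largest shortfall shifts the detectable standardised difference by only 0.511 − 0.50 = 0.011.

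**What to change.** Replace the drop-out sentence in section 10.2 and in the outline's Sample size row with:

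> Randomising 40 patients allows for up to 15% being non-evaluable for efficacy (34 evaluable, 81% power for d = 0.50). If 20% are non-evaluable, 32 remain and power is about 78%.

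This ties the allowance to the rule in section 10.3.8 and states the power at both ends of the range. The cost is one sentence in two places and a slightly less favourable stated power at the upper end. Enrolment, the randomisation list and drug supply do not change.

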10.3 Statistical analysis

10.3.1 Descriptive analysis

All the variables recorded in the Case Report Form will be reported in descriptive tables. In particular, continuous variables will be reported as a mean and SD, while nominal or discrete variables will be summarised in contingency tables.

10.3.2 Inferential statistics

The critical threshold of statistical significance for the tests shown below is P = 0.05.

10.3.3 Uniformity of the sequences to the baseline

To evaluate the uniformity of the two sequences, continuous parameters will be evaluated using the Student's t test for independent data, while the nominal or discrete parameters will be evaluated using the chi-square test with the continuity correction in the event of 2x2 tables.

10.3.4 Efficacy

The efficacy of Cetirizine in reducing FLS symptoms in patients with RRMS being treated with IFN β will be evaluated 4 hours after IFN β administration (after 4 weeks of therapy within each sequence)

The VAS and FLS-S score variables will be analysed using analysis of variance (ANOVA) with repeated measurements. In accordance with the crossover design of the study, the carry-over effect and the sequence effect will be evaluated in addition to the treatment effect.

During the treatment, the severity of the FLS, evaluated using both the VAS and FLS-S scores and recorded 4 and 12 hours after the injection, will be analysed using analysis of variance with repeated measurements. In accordance with the crossover design of the study, the carry-over effect and the sequence effect will be evaluated in addition to the treatment effect.

Moreover, appropriate multiple comparisons will be made to evaluate the time of the treatment between and within groups.

The same analysis in line with the crossover design will be performed on the values of the area under the curve (AUC) of the mean VAS and FLS-S values, recorded 4 and 12 hours after the injection for each treatment.

Lastly, the severity scores for flu-like syndrome (FLS-S) will be compared with the baseline scores. The patients for whom the score is increased by 2 or more units will be defined as positive for FLS and their frequencies will be analysed using the Armitage method, according to the crossover design.

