4 STUDY OBJECTIVES

To evaluate the effectiveness of the administration of cetirizine 10 mg in improving FLS symptoms.

The primary objective of the study is the mean variation in subjective severity of the FLS, evaluated according to the patient's judgment expressed on a visual analogue scale (FLS-VAS).

The secondary objectives are: the mean variation in severity of the FLS (evaluated based on the score of FLS symptoms (Flu-Like syndrome score (FLS-S))) between the findings before the injection, 4-6 hours after the injection and 12-15 hours after the injection of IFN β during the study period; the proportion of patients with a mean reduction of \geq 2 in FLS-S; and the incidence of FLS (defined as an increase of 2 or more FLS-S points compared to the value before the injection) 4-6 hours after the injection and 12-15 hours after the injection during the study period.

The safety and tolerability of the drug will be monitored for the entire duration of the study; in particular the most common adverse reaction to cetirizine (sleepiness), will be evaluated using the Epworth Sleepiness Scale (ESS) (Johns et al., 1991), validated in Italian (Vignatelli et al., 2003), at the baseline visit (V1), at 4 (V2) and 8 (V3) weeks (or at the final study visit - Vx).

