5 STUDY PLAN

5.1 Study design and operational plan outline

A randomised, monocentric, placebo-controlled, double-blind, crossover phase IIIb pilot study.

The patients will be randomised into a period of standard therapy plus cetirizine 10 mg lasting 4 weeks followed by 4 weeks of standard therapy plus placebo, or else in the opposite sequence. If the patient is already taking drugs for the treatment of FLS, for example paracetamol or ibuprofen, they must continue to maintain the dose of that therapy as stable as possible during the study period; this is defined by the protocol as the reference standard of therapy (SOT), at the discretion of the Investigator and in accordance with standard clinical practice.

The subjective severity of the FLS shall be evaluated by the patient expressed on a visual analogue scale (FLS-VAS). The FLS-VAS scale is 10 cm in length where 0 = No discomfort due to FLS and 10 = Maximum conceivable discomfort due to FLS.

Flu-Like Syndrome symptoms (muscle pain, chills and weakness) and body temperature will be evaluated using the FLS-S score.

To calculate FLS-S, patients must assign a score to the presence and intensity of muscle pain, chills and weakness, each separately, according to the following scale: 0 = absent; 1 = minor, has not interfered with daily activities; 2 = moderate, has interfered with normal activities; 3 = severe, requiring bedrest. In addition, the patient's body temperature will be recorded to ascertain whether fever is present using the following scale: $0: <37.3^{\circ}\text{C}$; $1: \ge 37.3^{\circ}\text{C}$ and $<37.8^{\circ}\text{C}$; $2: \ge 37.8^{\circ}\text{C}$ and $<38.4^{\circ}\text{C}$; $3: \ge 38.4^{\circ}\text{C}$. The scores for individual symptoms (muscle pain, chills, weakness and body temperature) will be added together to calculate the FLS-S, which will therefore vary between 0 and 12. A change in the total score ≥ 2 points above the pre-injection score has been predefined as positive for FLS.

All scores (FLS-VAS and FLS-S) will be recorded at three distinct times for each IFN β injection: baseline (when taking the study drug, 1 hour before the injection); Time A (4 hours after the

injection) and Time B (12-15 hours after the injection). All the scores and any analgesic doses taken will be noted in the patient diary.

The patients will record the data for each injection for 8 weeks.

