8.3 Storage and delivery of the study drug

The drug will be stored in the pharmacy or in another safe place at the study centre, at a temperature below 30°C. The drug must be kept in its original packaging to protect it from direct light. One capsule of cetirizine/placebo will be administered one hour before the IFNβ injection.

At visit V1, the Investigator shall give each patient the box showing the patient's randomisation number and the words: FIRST MONTH, containing a sufficient number of capsules to cover the number of Interferon injections to be given at the highest administration frequency (14 injections/month), and shall explain the administration and storage method. At visit V2, the Investigator shall collect the unused drug and the used blister cards and give the patient the box coded with the same randomisation number and the words SECOND MONTH. When dispensing the drug packages, the Investigator shall note the date of delivery and quantity of drug dispensed in the medical record and the Case Report Form. In addition, the date and quantity of the drug provided to each patient must be recorded on an accounting form provided by the selected CRO. At visit V3 the patient must return the previously received packages to the Investigator, whether

used or not. These packages shall then be sent to the Sponsor who shall ensure that they are destroyed.

Each patient will be given a diary in which he/she must record the dates on which the drug was taken. The Investigator shall check compliance at the visits specified by the protocol.

The Investigator shall record the date the drug is returned by the patient and the number of unused capsules in the accounting form.

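### The protocol does not fix one primary variable: objective, sample size and efficacy analysis describe the FLS-VAS outcome differently, and d = 0.50 is tied to none of them

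*Protocol*

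**What the plan says.** Four parts of the protocol bear on the primary variable.

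- **Section 4 (objectives):** "The primary objective of the study is the mean variation in subjective severity of the FLS", judged by the patient on the FLS-VAS. No post-injection hour, reference value or set of injections is given.
- **Section 1 (sample size) and Section 10.2:** the planning hypothesis concerns "four hours after administering IFN, the average difference (d) of the VAS score between the two treatments". Section 10.2 puts the standardised effect at 0.50, in units of the standard deviation of the difference. No pre-injection value is subtracted, and the injection or injections are not named.
- **Section 10.3.4 (efficacy):** efficacy is evaluated 4 hours after IFNβ, "after 4 weeks of therapy within each sequence". The section then plans a further repeated-measures analysis: "During the treatment, the severity of the FLS, evaluated using both the VAS and FLS-S scores and recorded 4 and 12 hours after the injection". It also plans a crossover analysis of the AUC of the mean VAS and FLS-S values. None of these is called primary.
- **Section 5.1 (data collected):** "The patients will record the data for each injection for 8 weeks", with scores before the injection, at Time A (4 hours) and at Time B (12-15 hours). Section 8.3 sizes the drug supply "at the highest administration frequency (14 injections/month").

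**The concern.** A change from the pre-injection score, a raw 4-hour score, a reading at the end of 4 weeks and a summary over all injections are different variables with different variances. A power statement in standard-deviation units has meaning only once the variable is named. As written, the 80% cannot be attached to any one of them.

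The choice also decides how much of the diary informs the primary test and how patients are weighted. Patients whose IFNβ is injected more often supply more readings, so pooling raw injections would give them more influence than a summary with one value per patient and period. In a trial of 40 patients with several unlabelled analyses, the protocol alone does not show which result decides whether the objective was met.

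**Working it through.** **1. The passages side by side**

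| Place | Raw score or change | Hour | Injections |
|---|---|---|---|
| Section 4, primary | variation, reference not given | not given | not given |
| Section 10.2 | score | 4 h | not given |
| Section 10.3.4, first analysis | score | 4 h | after 4 weeks (ambiguous) |
| Section 10.3.4, second analysis | score | 4 h and 12 h | during treatment |
| Section 10.3.4, AUC | mean values | 4 h and 12 h | per treatment |

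No row is complete enough to define a variable, and the rows do not reduce to one.

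**2. The plan's own sample size**

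The inputs from Section 10.2 are d = 0.50 (SD of the within-patient difference), two-sided α = 0.05, power 80% and n = 34. A paired t-test with noncentrality 0.50 × √34 = 2.92 and 33 degrees of freedom has power 80.8%, and 34 is the smallest n that reaches 80%. The stated figure reproduces. With 15% drop-out, 34 / 0.85 = 40, which also reproduces.

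**3. Readings left out if one end-of-period reading is used**

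- 14 injections per period (the maximum in Section 8.3): 13/14 = 93% of the 4-hour scores.
- 4 injections per period (weekly; an assumption, as the protocol gives no minimum): 3/4 = 75%.

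**4. What that could cost in power**

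Let r be the ratio of patient-by-period variance to injection-to-injection variance, and m the number of injections per period. Assume independent injection errors and the same mean treatment effect at each injection. The variance of the treatment difference for a mean of m readings, relative to one reading, is

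VR = (r + 1/m) / (r + 1).

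The protocol gives no variance components, so r is assumed to run from 0.25 to 9. Example for r = 0.25, m = 4: VR = (0.25 + 0.25) / 1.25 = 0.40.

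*Case A: d = 0.50 describes the period mean.* One reading then has d = 0.50 × √VR.

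| r | m | VR | d, one reading | Power, n = 34 | n for 80% |
|---|---|---|---|---|---|
| 0.25 | 4 | 0.400 | 0.32 | 43% | 81 |
| 0.25 | 14 | 0.257 | 0.25 | 30% | 125 |
| 1 | 4 | 0.625 | 0.40 | 61% | 53 |
| 1 | 14 | 0.536 | 0.37 | 54% | 61 |
| 9 | 4 | 0.925 | 0.48 | 78% | 36 |
| 9 | 14 | 0.907 | 0.48 | 77% | 37 |

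*Case B: d = 0.50 describes one reading.* One reading keeps 80.8%. The period mean has d = 0.50 / √VR. For r = 9 this is 0.52, with power 84% for both m = 4 and m = 14. For r = 1 it is 0.63 to 0.68, with power 95-97%. For r = 0.25 power is above 99%.

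The direction is certain under this model: a mean is never noisier than one reading. The size depends on r and on which summary d = 0.50 describes, and the protocol states neither.

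**The case against.** The strongest reply is that the texts are incomplete more than contradictory. Sections 1 and 10.2 and the first analysis in Section 10.3.4 all use a 4-hour VAS score compared between treatments, and the variation in Section 4 could simply mean that between-treatment difference. A statistical analysis plan, not shown here, may say how repeated injections are summarised. This has force against any claim that the endpoint will in fact be picked after unblinding. It does not remove the need to correct the protocol, whose sections give different or unfinished definitions and a phrase on timing that needs rewording.

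Several stronger readings are tempting, and the protocol does not support them.

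- *The primary is a change over the study period.* Those words in Section 4 belong to the secondary FLS-S objective: "12-15 hours after the injection of IFN β during the study period".
- *Efficacy is judged in period 1 only, because a sequence lasts 8 weeks.* The wording is careless, but Section 10.3.4 tests treatment, carry-over and sequence effects, and Section 10.3.8 requires evaluations under both products.
- *The last reading is certainly meant.* The phrase can equally mean an evaluation made once each 4-week period is complete. Diaries are collected at V2 and V3, and no clinic-visit VAS is scheduled.
- *Most of the diary is discarded.* Even on the end-of-period reading, the other scores enter the during-treatment and AUC analyses. They would be lost only to that one test.
- *Much of the power is lost.* With r = 9 the loss is 3 to 4 points in Case A, and in Case B the planned power is kept.

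**Conclusion.** The point holds in limited form. Sections 4, 10.2 and 10.3.4 do not define one primary variable, and the planned effect size is not tied to a stated summary. The sample size arithmetic itself is correct.

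If the efficacy wording is taken as an end-of-period reading, which is plausible but not certain, the primary test would omit up to 13 of 14 four-hour scores per period. The effect on power ranges from none (d = 0.50 describes one reading) to a fall from about 81% to between 30% and 78% (d = 0.50 describes the period mean). That range rests on assumed variance ratios of 0.25 to 9 and on 4 to 14 injections per period, the lower number also assumed. A reader should not infer that a large loss has been shown. What is shown is that the stated 80% belongs to no defined variable, and that this can be put right cheaply before unblinding.

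**What to change.** - In Sections 4, 10.2 and 10.3.4, state the same primary variable: for each patient and each 4-week period, the mean of the Time A (4-hour) FLS-VAS over all injections. This gives one equally weighted value per patient per period, compared between treatments under the crossover model.
- In Section 10.3.4, replace "after 4 weeks of therapy within each sequence" by wording that says over the 4 weeks of each treatment period.
- In Section 10.2 (and the outline), say that d = 0.50 refers to this period mean.
- Label the 12-15 hour, AUC and FLS-S analyses secondary, and keep the last-week reading as a sensitivity analysis.
- Do not adjust for the period mean of the pre-injection VAS. It is measured after earlier study doses in the same period and could absorb part of the treatment effect.

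The cost is an amendment to the text and a check that 0.50 is still a sensible effect size for the averaged variable. No new data are needed, because every injection is already scored in the diary. The small downside is that early injections of each period enter the mean; the last-week sensitivity analysis covers this.

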1 OUTLINE

	FLU-LIGHT Study - Flu L ike I nhibition G iving anti- H istaminic T herapy.			
Study title	A monocentric, randomised, placebo-controlled, double-blind crossover study to evaluate the efficacy of cetirizine on Flu-Like syndrome (FLS) in multiple sclerosis patients treated with interferon- β			
	BIIT 0212, pilot study phase IIIb.			
Study code and Phase	This is an interventional study that will be conducted in accordance with AIFA (Agenzia Italiana per il Farmaco [Italian Medicines Agency (IMA)]) and European clinical trials directives. The study is registered with EudraCT number 2013-001055-12.			
Study duration	The study will be conducted for at least 20 weeks (12 weeks for the enrolment period and 8 weeks for the treatment); each patient shall participate in the study for an overall period of 8 weeks of treatment with the study drug (4 with the active drug and 4 with a placebo).			
	Main objective:			
Objectives	Evaluate the efficacy of cetirizine 10 mg in reducing flu-like syndrome symptoms in patients with RRMS treated with IFNβ.			
	All patients already being treated with IFNs will be randomised into two sequences with cetirizine 10 mg and/or placebo, in a crossover study.			
	40 patients in treatment with IFN randomised into two sequences:			
	Sequence 1 (20 patients):			
Study Drug	first period (4 weeks) placebo			
	second period (4 weeks) cetirizine.			
	Sequence 2 (20 patients):first period (4 weeks) cetirizine			
	second period (4 weeks) placebo			
	8 weeks. After this period patients will continue their existing IFNβ treatment.			
	For each IFNβ injection			
	Baseline			
	FLS-VAS, Record symptoms and body temperature			
	Administer the study drug			
Treatment period	After one hour:			
P	Administer IFNβ			
	After 4 hours (Time A)			
	FLS-VAS, Record symptoms and body temperature			
	After 12/15 hours (Time B)			
	FLS-VAS, Record symptoms and body temperature			

Study design	A randomised, monocentric, placebo-controlled, double-blind, crossover phase IIIb pilot study.		

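### Section 10.3.4 names no baseline covariate for FLS-VAS or FLS-S although a pre-capsule reading is taken at every injection: precision that could be gained cheaply, not an error

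*Protocol*

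**What the plan says.** Section 10.3.4 fixes the efficacy method: "The VAS and FLS-S score variables will be analysed using analysis of variance (ANOVA) with repeated measurements". It adds that carry-over and sequence effects will be evaluated besides the treatment effect. A following paragraph applies the same method to the scores recorded 4 and 12 hours after the injection. No covariate is named. Within 10.3.4 the pre-injection value has one explicit use: classifying a patient as FLS-positive when FLS-S rises by 2 or more.

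The pre-injection value is nevertheless collected throughout. Section 5.1: "All scores (FLS-VAS and FLS-S) will be recorded at three distinct times for each IFN"β injection, the first being at capsule intake, one hour before the injection. The outline (section 1) lists the same item at baseline, Time A and Time B: "FLS-VAS, Record symptoms and body temperature".

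Section 4 gives the primary objective as "the mean variation in subjective severity of the FLS, evaluated according to the patient's judgment expressed on a visual analogue scale (FLS-VAS"). It does not say what the variation is measured from. For FLS-S, the same section does refer to findings before and after the injection.

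Section 10.2 sizes the trial on the 4-hour VAS. The standardised difference "is equal to or greater than 0.50, where d is expressed in standardized units", and the standardising SD is that of the within-patient difference. The conclusion is: "Selecting * = 0.05 and β = 0.20 (power =80%), it is necessary to enrol 34 patients".

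**The concern.** A crossover removes stable differences between patients. It does not remove changes within a patient from one 4-week period to the next, such as drift in MS-related weakness or muscle pain, both of which FLS-S scores. A pre-capsule reading in the same period can measure some of that drift. If it is left out of the model, whatever it would have explained stays in the SD of the within-patient difference, the quantity on which the trial is sized.

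The objective and the model also leave the role of the pre-injection value unsettled. Raw 4-hour scores, change from the pre-injection score, and adjusted scores are all compatible with some part of the text, and they differ in power. In a trial of 34 evaluable patients this choice is better fixed before unblinding, because a covariate added later can look data-driven.

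**Working it through.** **Inputs (section 10.2).** Two-sided α = 0.05, β = 0.20, d = 0.50 on the SD of the within-patient difference, n = 34 evaluable, 40 randomised. One input is not in the protocol: ρ, the correlation between the within-patient period difference in 4-hour VAS and that in pre-capsule VAS. It is assumed and shown as a range.

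**1. The plan's own figure.** Noncentral t on within-patient differences, with noncentrality d√n = 0.50 × √34 = 2.915. Power is 80.8% with 33 df and 80.7% with 32 df (period fitted). The smallest n reaching 80% is 34. The normal approximation gives (1.960 + 0.842)²/0.50² = 31.4, so 32. The stated 34 is reproduced.

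**2. Adding the covariate.** Adjustment multiplies the residual variance by (1 − ρ²). Estimating the slope inflates it by 1 + 1/(n − 4) = 1 + 1/30 and costs one further df (31 left). The effective standardised effect is

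d_adj = 0.50 / √[(1 − ρ²)(1 + 1/30)].

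For ρ = 0.5: 0.50/√(0.75 × 1.0333) = 0.568, noncentrality 0.568 × 5.831 = 3.31, power 89.4%.

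| ρ | d_adj | Power, n = 34 | Against 80.7% |
|---|---|---|---|
| 0 | 0.492 | 79.3% | −1.4 |
| 0.1 | 0.494 | 79.7% | −1.0 |
| 0.2 | 0.502 | 80.9% | +0.2 |
| 0.3 | 0.516 | 83.0% | +2.3 |
| 0.4 | 0.537 | 85.8% | +5.1 |
| 0.5 | 0.568 | 89.4% | +8.7 |
| 0.6 | 0.615 | 93.5% | +12.8 |

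A simulation of 6000 runs with period and treatment fitted gave adjusted power of 78.6%, 83.1% and 89.6% at ρ = 0, 0.3 and 0.5, in line with the table.

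**3. If variation means a simple change score.** Let k be the SD of the pre-capsule period difference divided by the SD of the 4-hour period difference. The variance relative to the raw score is 1 + k² − 2ρk, which exceeds 1 only when ρ < k/2. At ρ = 0.3:

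- k = 1: ratio 1 + 1 − 0.6 = 1.40, power 66.6%.
- k = 0.5: ratio 1 + 0.25 − 0.3 = 0.95, power 82.6%.

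The same correlation therefore gives a loss or a small gain, depending on k, which the protocol does not give.

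**4. Which pre-capsule reading.** Every reading after the first in a period follows earlier study capsules. Suppose 10% of the treatment effect leaks into a period-mean covariate (0.05 SD, k = 1). At ρ = 0.3 the adjusted effect becomes 0.50 − 0.3 × 0.05 = 0.485. Dividing by √(0.91 × 1.0333) = 0.970 gives 0.500, and with 31 df the power is 80.6%. The gain of 2.3 points is gone and the estimate is shrunk by 0.015/0.50 = 3%.

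**The case against.** The strongest reply is that nothing here is stated wrongly. The trial is sized on the unadjusted within-patient difference, the planned analysis matches that, and 34 reproduces. Covariate detail is commonly left to a statistical analysis plan, which is not shown. This stands in full against any claim of error. It does not remove the case for improvement, because section 10.3.4 already names the method and its terms, and section 4 leaves the response open.

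Second, the gain rests wholly on an undocumented ρ. Section 3 says symptoms generally begin 3–6 hours after the injection and resolve within 24 hours, so pre-capsule scores may sit near zero and predict little. This also stands: up to ρ of about 0.2 the gain is nil or slightly negative. A single first reading per period is likely to correlate less with the 4-hour scores than a period mean would.

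Third, the wording does not exclude the pre-injection value from the model. The sentence quoted from 10.3.4 is not limited to post-injection scores, so a repeated-measures ANOVA with the pre-injection time as a level is a possible reading. That is fair, and it is a reason to state the response plainly.

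Fourth, the covariate has its own weakness. A period mean is partly post-treatment, and the first reading of period 2 follows period 1 without wash-out (section 5.2). The 24-hour resolution and the maximum of 14 injections a month (section 8.3) suggest that contamination is small, but they do not show it.

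A reader might also infer that a change score is inefficient whenever the correlation is below 0.5. That holds only for equal SDs (k = 1). The threshold is k/2, so no general 0.5 rule should be claimed.

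**Conclusion.** The point holds as forgone precision. A reading that could serve as a period-specific covariate is collected at every injection, and the model in 10.3.4 names none. A reader might infer that the trial is underpowered or that the 80% is wrong. The documents do not support that: the unadjusted analysis has 80.7% power at 34. Nor do they show that power is in fact lost, since that depends on ρ.

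At 34 patients the effect of adjusting runs from about −1.4 points (ρ = 0) through +2.3 (ρ = 0.3) to +8.7 (ρ = 0.5), and reaches 5 points only at ρ of about 0.4. These figures assume d = 0.50 on the SD of the difference, a linear relation, and a covariate unaffected by treatment. The possible loss is small and bounded and the possible gain is larger, so the change is worth making. It is an improvement, not a correction.

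**What to change.** In section 10.3.4:

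- Name the 4-hour FLS-VAS as the primary response, and align the wording of section 4 with it.
- Analyse it by crossover ANCOVA, with the period-specific pre-capsule FLS-VAS entered as a within-patient covariate (period 1 minus period 2). Do the same for FLS-S.
- Use the first pre-capsule reading of each period as the main covariate, because later readings follow earlier study capsules.
- Report two sensitivity analyses: the model with the period-mean pre-capsule reading, and the unadjusted model.

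This changes wording only, needs no new data, and should be settled before unblinding. It costs one degree of freedom and up to about 1.5 points of power if the baseline proves uninformative. One limit remains: the first reading of period 2 follows period 1 without wash-out, so in patients who took cetirizine first it could still carry some treatment effect.
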